8.2.2 VRC07-523LS

VRC07-523LS will be supplied as 10 mL single-use glass vials with a 6.25 ± 0.1 mL fill volume and 3 mL single-use glass vials with a $2.25 \text{ mL} \pm 0.1$ mL fill volume, at a concentration of 100 ± 10 mg/mL. Each vial contains a clear, colorless to yellow liquid, essentially free of visible particles; some opaque or translucent particles may be present. The formulation buffer is composed of 50mM histidine, 50 mM sodium chloride, 5% sucrose, and 2.5% sorbitol at pH 6.8. Vials do not contain a preservative.

VRC07-523LS product label designates the long-term storage as -35°C to -15°C (-31°F to 5°F). The study product is described in further detail in the IB.

8.2.3 PGT121.414.LS

PGT121.414.LS will be supplied as 10 mL single-use glass vials with a 4.75 mL fill volume, at a concentration of 100 mg/mL. Each vial contains a clear, colorless to yellow, preservative free, sterile solution for injection. The formulation buffer is composed of acetate, sucrose, polysorbate 80 at pH of 5.2. PGT121.414.LS product label designates the long-term storage as -35°C to -15°C (-31°F to 5°F).

8.3 Preparation of study products

Prior to preparation of the first infusion (enrollment visit), a new prescription will be sent to the pharmacy. For participants randomized to a weight-based (mg/kg) dosing group, the prescription MUST contain the participant's weight based upon the participant's weight at the most recent visit where weight was measured (this includes screening). If this information is NOT on the prescription, the prescription will be returned to the clinic from the pharmacy to be completed appropriately prior to the pharmacist beginning preparation of study product. Subsequent visit weights (based upon the participant's weight at the most recent visit where weight was measured) must be communicated to the pharmacy in

writing prior to the day of the visit. Any changes in weight of more than 10% (between the prior weight and the weight on the day of the infusion visit) will require an updated visit weight communication to the pharmacy in writing so that product can be prepared based on that weight change.

For Groups 8 and 9, the prescription will be written as the fixed dose per the randomized dose assignment.

For Groups 3, 5, 7 and 9, the prescription must also contain the number of infusion sites that will be used for each study product. The prescription may also need to contain additional information (eg, amount of overfill the syringe must contain to account for residual volume in the tubing), depending on the tubing and pump to be used for study product administration. See HVTN 140/HPTN 101 SSP for more details.

Pharmacists must follow appropriate aseptic technique and sterile preparation procedures as outlined in United States Pharmacopeia (USP) <797> Pharmaceutical Compounding – Sterile Preparations, utilizing a pharmacy biosafety cabinet/isolator or better. Local regulations and site institutional policies and procedures for use of personal protective equipment such as gloves, gowns, masks, and safety glasses, must be followed. Pharmacists should follow the requirements of their country, their institution, and their pharmacy regulatory authority regarding these procedures.

Any unused portion of study product will not be used for another participant. Any empty vials, unused portion of entered vials, or unused solution which contains study product should be discarded in a biohazard containment bag and incinerated or autoclaved in accordance with institutional or pharmacy policy.

8.3.1 PGDM1400LS

8.3.1.1 Thawing instructions

1. Remove PGDM1400LS vials from the freezer and thaw at controlled room temperature (maximum 27°C).
2. After thawing, the PGDM1400LS vials may be stored at 2°C to 8°C for up to 48 hours and/or at 15°C to 27°C for up to 24 hours. Product may not be stored in direct sunlight. If stored at 2°C to 8°C, vials must be equilibrated at controlled room temperature (15°C - 27°C) for a minimum of 30 minutes and may be held at room temperature for up to 8 hours prior to product preparation. PGDM1400LS vials should not be refrozen after thaw.

8.3.1.2 PGDM1400LS weight-based dose intravenous infusion preparation

1. Calculate the total dose (mg) of PGDM1400LS required based on the participant's weight (in kg). Obtain the minimum number of thawed

PGDM1400LS vials, as well as an appropriately sized IV container (bag/glass bottle) containing 100 mL of 0.9% Sodium Chloride for Injection, USP, that will also permit the addition of the required calculated volume of PGDM1400LS.

2. Using an 18G needle, withdraw the calculated volume of PGDM1400LS into a sterile syringe.
3. Using aseptic technique, remove the air from the IV container and then add the withdrawn volume of PGDM1400LS to the IV container with 100 mL of 0.9% Sodium Chloride for Injection, USP. Record this as the study product preparation time.
4. Gently mix the prepared IV container. Ensure there are no visible particulates in the IV container.
5. After product preparation in IV bags, the prepared PGDM1400LS product may be stored at 2°C to 8°C up to 24 hours and/or at controlled room temperature (15°C - 27°C) for a maximum of 4 hours total including the infusion time. Product may not be stored in direct sunlight. If stored at 2°C to 8°C, prepared product must be equilibrated at controlled room temperature (15°C - 27°C) for a minimum of 30 minutes prior to product administration.

8.3.1.3 PGDM1400LS fixed-dose intravenous infusion

1. Obtain 4 vials of thawed PGDM1400LS vials, as well as an appropriately sized IV container (bag/glass bottle) containing 100 mL of 0.9% Sodium Chloride for Injection, USP, that will also permit the addition of the required calculated volume of PGDM1400LS.
2. Using an 18G needle, withdraw a total of 14 mL of PGDM1400LS into a sterile syringe.
3. Using aseptic technique, remove the air from the IV container and then add the withdrawn 14 mL of PGDM1400LS to the IV container with 100 mL of 0.9% Sodium Chloride for Injection, USP. Record this as the study product preparation time.
4. Gently mix the prepared IV container. Ensure there are no visible particulates in the IV container.
5. After product preparation in IV bags, the prepared PGDM1400LS product may be stored at 2°C to 8°C up to 24 hours and/or at controlled room temperature (15°C - 27°C) for a maximum of 4 hours total including the infusion time. Product may not be stored in direct sunlight. If stored at 2°C to 8°C, prepared product must be equilibrated at controlled room

temperature (15°C - 27°C) for a minimum of 30 minutes prior to product administration.

8.3.1.4 PGDM1400LS weight-based dose subcutaneous infusion preparation

1. Calculate the total dose (mg) of PGDM1400LS required based on the participant's weight (in kg). Remove the minimum number of thawed PGDM1400LS vials from storage.
2. Using aseptic technique, withdraw the calculated volume of PGDM1400LS from the vial(s) into a syringe using a 5-micron filter needle (see HVTN 140/HPTN 101 SSP for needle/filter specifications and details). A new filter needle must be used for each vial. Add the additional volume of PGDM1400LS needed to accommodate for the residual volume left in the tubing after infusion. Discard the filter needle(s) prior to dispensing. Record this as the study product preparation time.
3. After preparation in syringes for SC administration, the prepared PGDM1400LS product may be stored at 2°C to 8°C up to 24 hours or at controlled room temperature (15°C - 27°C) up to 4 hours including administration time. Product may not be stored in direct sunlight. If stored at 2°C to 8°C, prepared product must be equilibrated at controlled room temperature (15°C - 27°C) for a minimum of 30 minutes prior to product administration.

8.3.1.5 PGDM1400LS fixed-dose subcutaneous infusion preparation

1. Remove 4 vials of thawed PGDM1400LS vials from storage.
2. Using aseptic technique, withdraw 14 mL of PGDM1400LS from the vial(s) into a syringe using a 5-micron filter needle (see HVTN 140/HPTN 101 SSP for needle/filter specifications and details). A new filter needle must be used for each container. Add the additional volume of PGDM1400LS needed to accommodate for the residual volume left in the tubing after infusion. Discard the filter needle prior to dispensing. Record this as the study product preparation time.
3. After preparation in syringes for SC administration, the prepared PGDM1400LS product may be stored at 2°C to 8°C up to 24 hours or at controlled room temperature (15°C - 27°C) up to 4 hours including administration time. Product may not be stored in direct sunlight. If stored at 2°C to 8°C, prepared product must be equilibrated at controlled room temperature (15°C - 27°C) for a minimum of 30 minutes prior to product administration.

8.3.2 VRC07-523LS

VRC07-523LS is a highly concentrated protein solution and may develop white, opaque to translucent particles after thawing.

8.3.2.1 Thawing instructions

1. Thaw vial(s) for a minimum of 1 hour at controlled room temperature (maximum 27°C) after removing from the freezer.
2. Keep the material at room temperature during the entire preparation period until use, up to the maximum storage times described in # 4 below.
3. Prior to preparation for administration, swirl vials for 30 seconds to resuspend any visible particles, avoid foaming. DO NOT SHAKE THE VIALS. If particles are observed, return the vials to 2°C to 8°C storage. If the particles re-dissolve within the maximum storage times described in # 4 below, they may be used for product preparation. If particles continue to be observed, do not use the vials.
4. Thawed vials may be stored for up to 24 hours at controlled room temperature (maximum 27°C) and/or up to 2 weeks (14 days) at 2°C to 8°C. Product may not be stored in direct sunlight. If stored at 2 °C to 8 °C, vials must be equilibrated at controlled room temperature (maximum 27 °C) for a minimum of 30 minutes and may be held at room temperature for up to 8 hours prior to product preparation.

8.3.2.2 VRC07-523LS weight-based dose intravenous infusion preparation

1. Calculate the total dose (mg) of VRC07-523LS required based on participant's weight (in kg). Remove the minimum number of thawed particle free VRC07-523LS vials from storage, as well as an appropriately sized IV container (bag/glass bottle) containing 100 mL of 0.9% Sodium Chloride for Injection, USP, that will also permit the addition of the required calculated volume of VRC07-523LS.
2. Gently swirl thawed vials for 30 seconds, avoiding foaming. DO NOT SHAKE VIALS. Keep the vials upright at all times until ready to withdraw the contents. Do not invert the vials during inspection.
3. Observe vials for particles. If particles are observed, refer to the thawing instructions described above in Section 8.3.2.1.
4. Using aseptic technique, add the calculated volume of VRC07-523 LS to the IV container with 100 mL of Sodium Chloride for Injection, 0.9 USP. Record this as the study product preparation time.
5. The prepared VRC07-523LS IV container may be stored at 2°C to 8°C up to 48 hours or at controlled room temperature (maximum 27°C) for a

maximum of 4 hours total including the infusion time. Product may not be stored in direct sunlight. If stored at 2°C to 8°C, prepared product must be equilibrated at controlled room temperature (maximum 27°C) for a minimum of 30 minutes prior to product administration.

8.3.2.3 VRC07-523LS fixed-dose intravenous infusion preparation

1. Remove either three 10 mL vial sizes or eight 3 mL vial sizes of thawed particle free VRC07-523LS from storage, as well as an appropriately sized IV container (bag/glass bottle) containing 100 mL of 0.9% Sodium Chloride for Injection, USP, that will also permit the addition of the required calculated volume of VRC07-523LS.
2. Gently swirl thawed vials for 30 seconds, avoiding foaming. DO NOT SHAKE VIALS. Keep the vials upright at all times until ready to withdraw the contents. Do not invert the vials during inspection.
3. Observe vials for particles. If particles are observed, refer to the thawing instructions described above in Section 8.3.2.1.
4. Using aseptic technique, add 14 mL of VRC07-523 LS to the IV container with 100 mL of 0.9% Sodium Chloride for Injection, USP. Record this as the study product preparation time.
5. The prepared VRC07-523LS IV container may be stored at 2°C to 8°C up to 48 hours or at controlled room temperature (maximum 27°C) for a maximum of 4 hours total including the infusion time. Product may not be stored in direct sunlight. If stored at 2°C to 8°C, prepared product must be equilibrated at controlled room temperature (maximum 27°C) for a minimum of 30 minutes prior to product administration.

8.3.2.4 VRC07-523LS weight-based dose subcutaneous infusion preparation

1. Calculate the total (mg) of VRC07-523LS required based on the participant's weight (in kg). Remove the minimum number of thawed particle-free VRC07-523LS vials from storage.
2. Gently swirl thawed vials for 30 seconds to avoid foaming. DO NOT SHAKE VIALS. Keep the vials upright until ready to withdraw the contents. Do not invert the vial during inspection.
3. Observe vials for particles. If particles are observed, refer to the thawing instructions described above in Section 8.3.2.1.
4. Using aseptic technique, withdraw the calculated volume of VRC07-523LS from the vial(s) into a syringe using a 5 micron filter needle (see HVTN 140/HPTN 101 SSP for needle/filter specifications and details). A

new filter needle must be used for each vial. Discard the filter needle prior to dispensing. Record this as the study product preparation time.

5. The prepared VRC07-523LS syringe(s) may be stored at 2°C to 8°C for up to 24 hours or at controlled room temperature (maximum 27°C) for a maximum of 4 hours, including the administration time. Product may not be stored in direct sunlight. If stored at 2°C to 8°C, prepared product must be equilibrated at controlled room temperature (maximum 27°C) for a minimum of 30 minutes prior to product administration.

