8.3.2.5 VRC07-523LS fixed-dose subcutaneous infusion preparation

1. Remove either three 10 mL vial sizes or eight 3 mL vial sizes of thawed particle free VRC07-523LS from storage.
2. Gently swirl thawed vials for 30 seconds, avoiding foaming. DO NOT SHAKE VIALS. Keep the vials upright at all times until ready to withdraw the contents. Do not invert the vials during inspection.
3. Observe vials for particles. If particles are observed, refer to the thawing instructions described above in Section 8.3.2.1.
4. Using aseptic technique, withdraw 14 mL of VRC07-523 LS into a syringe using a 5 micron filter needle (see HVTN 140/HPTN 101 SSP for needle/filter specifications and details). A new filter needle must be used for each vial. Add the additional volume of VRC07-523LS needed to accommodate for the residual volume left in the tubing after infusion. Discard the filter needle prior to dispensing. Record this as the study product preparation time.
5. The prepared VRC07-523LS syringe(s) may be stored at 2°C to 8°C for up to 24 hours or at controlled room temperature (maximum 27°C) for a maximum of 4 hours, including the administration time. Product may not be stored in direct sunlight. If stored at 2°C to 8°C, prepared product must be equilibrated at controlled room temperature (maximum 27°C) for a minimum of 30 minutes prior to product administration.

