8.4 Administration

For weight-based dosing, the container prepared by the pharmacy will include the weight that was used for preparation of the study product. The clinician responsible for administration will check the container label and confirm that the participant identifier(s) is/are correct and that the weight listed on the container label is within 10% of the participant's current actual weight.

In Groups 6-10, three separate IV containers each containing one study product will be administered sequentially.

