8.4.1 General considerations for subcutaneous infusion study product administration

Due to factors such as dose and volume, participant weight and body habitus, and participant tolerability and preference, the site clinicians and participants must decide whether to subcutaneously infuse each study product at 1, 2, or 3 anatomic locations simultaneously. In Part B, three mAbs are infused sequentially; thus in Part B there are a minimum of 3 and a maximum of 9 infusion sites. The HVTN 140/HPTN 101 SSP provides information about subcutaneous infusion sets, recommended infusion pumps and clinical considerations for study product administration.

A suitable SC infusion set (tubing and needle(s)) should be affixed to the syringe prior to administration. The SC infusion sets are carefully and gently primed with the study product just to the end of the tubing leaving the needle dry. Dry needles are less painful. The syringe will be prepared with overfill to accommodate for the residual study product left in the tubing.

Refer to the HVTN 140/HPTN 101 SSP for further information on SC administration.

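### The weight-based subcutaneous preparation of VRC07-523LS (Group 7 only) leaves out the tubing-overfill step that the other five subcutaneous preparations carry, so that one antibody could be under-delivered

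*Protocol*

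**What the plan says.** The protocol has six subcutaneous preparation sections, a weight-based and a fixed-dose one for each antibody. For weight-based VRC07-523LS (Section 8.3.2.4, step 4) the pharmacist is to "withdraw the calculated volume of VRC07-523LS from the vial(s) into a syringe using a 5 micron filter needle". The step then says that a "new filter needle must be used for each vial. Discard the filter needle prior to dispensing". Nothing between those two instructions adds volume for the tubing.

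The fixed-dose section for the same product (8.3.2.5) includes the step at that point: "Add the additional volume of VRC07-523LS needed to accommodate for the residual volume left in the tubing after infusion". The weight-based PGDM1400LS section (8.3.1.4) has the matching sentence: "Add the additional volume of PGDM1400LS needed to accommodate for the residual volume left in the tubing after infusion". Sections 8.3.1.5, 8.3.3.4 and 8.3.3.5 carry it as well.

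Section 8.4.1, on subcutaneous administration in general, says "The SC infusion sets are carefully and gently primed with the study product just to the end of the tubing" and that "The syringe will be prepared with overfill to accommodate for the residual study product left in the tubing". For Groups 3, 5, 7 and 9, Section 8.3 has a provision that turns on the equipment chosen; it says of the written order that it "may also need to contain additional information (eg, amount of overfill the syringe must contain to account for residual volume in the tubing").

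Under Section 8.1, Group 7 is the only group given weight-based subcutaneous VRC07-523LS. Groups 3 and 5 receive PGDM1400LS alone, and Group 9 is fixed dose.

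**The concern.** Because the infusion set is primed with study product, whatever stays in the tubing at the end is not delivered unless the syringe held extra. A pharmacist who follows Section 8.3.2.4 step by step draws the nominal dose and no more, while the two companion antibodies for the same Group 7 visit are prepared under sections that require overfill.

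The shortfall would fall on one antibody in one randomized arm, always in the same direction. It would lower VRC07-523LS concentrations in Group 7 against Group 9 (weight-based against fixed dose, both subcutaneous) and against Group 6 (subcutaneous against intravenous), and so make subcutaneous bioavailability look lower than it is. A roughly constant residue also takes a larger share of a small dose than of a large one, which would imitate a body-weight effect in Secondary objective 4.

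An unrecorded shortfall would pass through the per-protocol concentration analysis, since the participant would appear to have received the expected dose. The secondary analyses that account for actual dose amount (Protocol 6.4, SAP 8) could correct it only if it had been recorded.

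**Working it through.** **Text comparison**

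| Section | Product and dosing | Overfill step |
|---|---|---|
| 8.3.1.4 | PGDM1400LS, weight-based | Yes |
| 8.3.1.5 | PGDM1400LS, fixed | Yes |
| 8.3.2.4 | VRC07-523LS, weight-based | No |
| 8.3.2.5 | VRC07-523LS, fixed | Yes |
| 8.3.3.4 | PGT121.414.LS, weight-based | Yes |
| 8.3.3.5 | PGT121.414.LS, fixed | Yes |

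The calculated volume cannot be read as already containing the overfill: Sections 8.3.1.4 and 8.3.3.4 use the same term and then add the overfill separately.

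**Inputs.** Dose 20 mg/kg (8.1, Group 7); nominal concentration 100 mg/mL (8.2.2); eligible weight 35 to 115 kg (7.2); n = 12 per group and log-scale SD 0.5 (6.1.2). The residual volume r is not in the documents; 0.5, 1 and 2 mL are assumed.

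**Check on volume.** 1,400 mg / 100 mg/mL = 14 mL, which matches the fixed-dose volume in the protocol.

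**Dose volume and loss without overfill.** Volume = weight × 20 / 100. Loss = r / volume.

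| Weight | Volume | r = 0.5 mL | r = 1 mL | r = 2 mL |
|---|---|---|---|---|
| 35 kg | 7 mL | 7.1% | 14.3% | 28.6% |
| 70 kg | 14 mL | 3.6% | 7.1% | 14.3% |
| 115 kg | 23 mL | 2.2% | 4.3% | 8.7% |

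**Shift in log concentration at 70 kg**, assuming concentration proportional to dose: ln(1 − r/14) = −0.036, −0.074 and −0.154 for r = 0.5, 1 and 2 mL.

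**Precision of a two-group comparison.** 95% half-width = t(0.975, 22 df) × 0.5 × √(2/12) = 2.074 × 0.5 × 0.408 = 0.423 on the log scale. The shift is therefore about 9% to 36% of the half-width (0.036/0.423 to 0.154/0.423).

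**False weight exponent in Group 7, 35 to 115 kg.** [ln(1 − r/23) − ln(1 − r/7)] / ln(115/35), with ln(115/35) = 1.190:
- r = 0.5 mL: (−0.022 + 0.074) / 1.190 = 0.044
- r = 1 mL: (−0.044 + 0.154) / 1.190 = 0.092
- r = 2 mL: (−0.091 + 0.336) / 1.190 = 0.206

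With the overfill step in place, the volume drawn is the dose volume plus r and the shortfall is zero.

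**The case against.** The strongest reply is that the protocol, read as a whole, already requires overfill. Section 8.4.1 makes no exception by product or group, and Section 8.3.2.4 is silent rather than contrary. The prescription wording in Section 8.3 covers Group 7 and depends on the tubing and pump, not on the antibody. The pharmacist will be preparing two companion syringes with overfill for the same visit. The protocol also refers to the Study Specific Procedures for subcutaneous details, and these may specify the overfill. All of this makes an actual shortfall less likely and is why the point is conditional.

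It does not remove the inconsistency. Section 8.4.1 sits under administration, whereas the pharmacist's numbered steps are in Section 8.3, and the prescription provision is only permissive. The bedside check does not catch the error: the clinician is to "confirm that the participant identifier(s) is/are correct and that the weight listed on the container label is within 10" per cent of current weight. The label shows total dose and final volume, but no stated check compares them with the overfill needed.

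The objections on size partly stand. The residual volume is assumed, and 28.6% needs the top of that range in a participant at the minimum weight. The exponent is taken between the eligibility limits; the local slope at 70 kg, r/(14 − r), is smaller (0.037, 0.077 and 0.167). Group 7 is 16 of 80 Part B participants, so a pooled covariate model would dilute the effect. The primary concentration analysis is descriptive, and no powered comparison of Group 7 with Group 9 or Group 6 is specified.

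The mid-range loss of 7.1% at 70 kg also lies within tolerances the protocol accepts (±10 mg/mL on concentration, 10% on weight). Those tolerances, however, are not a one-directional error confined to one antibody in one arm.

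**Conclusion.** The concern holds. Section 8.3.2.4 is the only one of six subcutaneous preparation sections without the overfill step, and it is at odds with Section 8.4.1. Nothing suggests a deliberate exception; it reads as a drafting omission in an operative dosing instruction.

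Whether any dose would be short cannot be established from the protocol and SAP. If the steps were followed literally, and 0.5 to 2 mL stayed in the tubing, the effect on the Group 7 mean would be modest and would not decide a comparison by itself. It would still be a systematic and avoidable bias, heaviest in the lightest participants and aligned with the weight question in Secondary objective 4. It should be corrected, but it does not threaten the trial.

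**What to change.** In Section 8.3.2.4, step 4, after the instruction to change the filter needle for each vial and before the instruction to discard it, insert the sentence already used in Section 8.3.2.5: "Add the additional volume of VRC07-523LS needed to accommodate for the residual volume left in the tubing after infusion". This brings the section into line with the other five and with Section 8.4.1.

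The cost is one sentence in a clarification memo, a route Section 13 already provides for, and a small amount of extra VRC07-523LS per Group 7 dose. Sample size, visits and analysis do not change.
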